Based on previous data, we anticipate that we will be able to identify at least 50 adolescents per clinic for a total of at least 5000 adolescents. Assuming a prevalence of 60%, an intra-class coefficient (ICC) of 0.05 and a clinic size of 50 we would need to select 102 clinics for estimating the expected proportion with a 2.5% absolute precision and 95% confidence. With a sample size of 5,000 adolescents who are enrolled in HIV care during the previous 12-24 months, the precision of the estimates across possible ranges (50%-90%) of prevalence of retention in care or viral load suppression will range from $\pm 2.6\%$ to $\pm 1.5\%$ (Table 5). Thus, with 5000 adolescents or more, our study will have high precision in estimating the prevalence of retention in care and HIV viral load suppression, providing valuable input for understanding impact of interventions aimed at improving these adolescent HIV outcomes.

Table 7: Precision estimates for prevalence of retention and viral load suppression in HIV-infected adolescents

Indicator	Adolescents evaluated	Observed Prevalence	Events	CI	Precision
Retention or suppressed viral load	5000	50%	2500	47.4-52.6%	+/-2.6%
	5000	60%	3000	57.5-62.5%	+/-2.5%
	5000	70%	3500	67.6-72.4%	+/-2.4%
	5000	80%	4000	77.9-82.1%	+/-2.1%
	5000	90%	4500	88.5-91.5%	+/-1.5%

Aim 2: Given that the goal of the interviews conducted in this aim is to gather information on experiences with disclosure and transition and use this information to refine study tools, we believe that conducting 16 focus group discussions with adolescents (N=96), 16 focus group discussions with primary caregivers of adolescents (N=48), 38 interviews with HCWs and 30 interviews with administrators and policy makers, will give us adequate numbers to reach our study goal and enough diversity in experiences to ensure different perspectives are accurately represented in study tool refinement. A working group comprised of approximately 40 HCWs with significant expertise in providing care for HIV-infected children, adolescents and adults will be

sufficient to foster rich discussions around study tools. Including approximately 40 HCWs, will allow participation of all stakeholders.

Aim 3: For the RCT, using a conservative estimate of 20% of clients being between 10-24 years old and each clinic having at least 500 active clients, we anticipate 200 eligible clients per clinic, for a total of 1000 eligible clients per randomization arm.

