- We assume that 100 of these eligible clients will be aged 6-15 and that the rate of complete disclosure will be 15% in the control clinics based on our prior studies and the literature with increased prevalence per year of age in this age-window.
- We assume that 100 of these eligible clients will be aged 15-24 years and that 20% (n=20) will be receiving care in a pediatric program and could be eligible to transition (200 per RCT arm). During 2-year follow-up, we anticipate that in the control arm 20% will transition and 10% will transition effectively.

With 10 intervention and 10 control sites, we will have sufficient power to detect an increase in proportion of adolescents with disclosure from 30% to 50%, an increase in proportion who initiate transition from 50% to >80%, and an increase in proportion with effective transition from 10% to 20%. This assumes alpha of 0.05, 80% power, and a conservative estimate of the coefficient of variation of 0.3 (Table 6). Heterogeneity between clusters is expected to decrease with control for baseline testing rates, leading to increased power beyond that which is noted above.

Table 8: Power and sample size ranges

	Outcome Control	Outcome Intervention	Number of clinics per RCT arm to detect difference
Age 10-15	N=1000 (100/clinic)	N=1000 (100/clinic)	
Disclosure process started (proportion)	50% 50% 50%	>80% >90% 100%	9 6 5
Disclosure complete (proportion)	30% 30% 30%	50% 70%	8 4 3
Disclosure age median	14 years old	12 years old	NA
24-month LTFU	20%	10%	7
Age 16-24	N=1000 (100/clinic)	N=1000 (100/clinic)	
Transition discussed (proportion)	20% 20% 50%	40% 60% 100%	6 3 5
Transition complete (proportion)	10%	20%	7
Transition satisfaction	50%	70%	NA
24-month LTFU	25%	15%	10

For the provider and adolescent IDIs, we will select healthcare providers and adolescents from ATP-implementing clinics for individual interviews. Clinics will be purposively selected from among all ATP-implementing clinics. We will purposively select clinics for interviews based on performance, including high and low performing sites as appropriate based on the outcome of the intervention. If the majority of clinics do well, we will purposively select a higher proportion of low performing clinics to understand why they had challenges. If the majority of the clinics do poorly, we will purposively select a higher proportion of high performing clinics to understand how they succeeded.

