Recruitment Scripts:

Study Activity	Recruitment Script
Aim 1`	
Facility Survey	Facility Survey Recruitment Script
Aim 2	
Adolescents in HIV care (48 not completed transition, 48 transitioned)	NA
	Caregiver recruitment script for adolescent IDI and FGD
	Adolescent recruitment script
Caregivers	Caregiver recruitment script
Policy makers	Policy maker/Admin/HCW recruitment script
HCW/Administrator	Policy maker/Admin/HCW recruitment script
Working group	HCW recruitment script for Workshop
Aim 3	
Pre-Trial surveys	Adolescent Recruitment Script*
Implementation Activities	HCW IS Activities Recruitment Script
Post-trial IDI	NA
	Adolescent recruitment script*
	Caregiver recruitment script*
	HCW recruitment script*
Implementation FGDs	HCW FGD Recruitment Script
Transition readiness	Adolescent recruitment script*
Disclosure readiness	Caregiver recruitment script
Post-trial surveys	Adolescent recruitment script*
	HCW recruitment script*

*Same as aim 2 document

ATTACH STUDY ANALYSIS PLAN (Finalized 2.13.2020)

SUMMARY

Study Purpose: To determine whether an adolescent transition package (with transition and disclosure tools) improves **mean transition readiness** among HIV positive adolescents in care in Kenya.

Study Design: Cluster randomized trial

Study Population and Sites:

Population:

- HIV-positive adolescents and youth between the ages of 10 and 24

Sites:

- 20 HIV clinics in Nairobi, Nakuru, Homabay and Kajiado, Kenya

Study Duration: Estimated 18 months total (enrollment and 1-year follow-up)

Randomization: 10 clinics randomized to intervention sites and 10 to control.

Intervention:

Adolescent Transition Package (ATP): The ATP will consist of a validated disclosure booklet and disclosure tracking tool, and a HCW administered transition booklet and transition tracking logs, implemented in intervention sites. HCW in intervention sites will be trained on implementation of the ATP with continued support for the clinic in the first 3 months of the intervention. In control sites, parallel data collection for primary outcomes will be conducted.

Primary endpoints: Transition readiness

Secondary endpoints: Overall clinic retention and overall viral suppression

Exploratory outcome: % with full disclosure, Time to full disclosure, Post transition retention

DATA ANALYSIS

Primary outcome: transition readiness among HIV positive adolescents age 15-24

- a. Transition readiness score overall (all domains)
- b. Treatment literacy readiness score

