- c. Self-management readiness score
- d. Communication readiness score
- e. Support readiness score

Analysis

Primary analysis ITT: Mixed effects linear regression to compare transition readiness scores (overall and by domain) over time in control and intervention sites with adjustment for multiple testing (Benjamin-Hochberg method).

Time points: Enrollment, month 6, month 12

Sample size and power table

Assumptions: 80% power, alpha 0.05, ICC 0.2, average cluster size of 50

Mean difference	SD	Number of Clusters per Arm
0.5	1	4
0.5	2	15
1.0	2	4
1.0	3	9
1.5	3	4
1.5	4	7
2.0	5	6
2.0	6	9

Secondary outcomes

- a. Overall retention in 10-24 year olds: defined as proportion of 10-24 year olds completing visits within 6 months of last visit
- b. Overall viral suppression: defined as proportion of 10-24 year olds with viral load of less than 1000 copies per ml after at least 6 months of ART

Analysis

Overall retention/suppression: Generalized estimating equations (GEE) to compare retention and viral suppression in intervention and control sites

Time-points: Baseline, month 6, month 12

Minimum detectable differences in proportions with outcomes

Assumption: 80% power, alpha 0.05, ICC 0.2, 10 clusters per arm, average cluster size of 50

Proportion with outcome in arm 1	Proportion with outcome in arm 2
0.2	0.31
0.3	0.44
0.4	0.56

0.5	0.69
0.6	0.81
0.7	0.93

Exploratory analyses

1. Post-transition retention defined as completing and adult clinic visit day after transfer to adult services and at least 1 other visit within 6 months of the adult visit (total of 2 visits):
Analysis: GEE to compare post-transition retention in intervention and control sites
2. Principal components analysis to identify the most representative components of data in the 4 domains of the readiness assessment checklist (HIV treatment literacy (Q 1-5), self-management (Q6, 7, 9-14, communication Q16-19, support 20-22) and then factor analysis to determine the most important components.
3. Proportion of children with full disclosure and time to full disclosure. Children who do not know their HIV status from HCW assessment. Child will be asked why they are taking medicine; if they report they have HIV they have reached full disclosure. If they mention any other illness or other responses they will not have reached full disclosure.
End point: Child says they have HIV in response to the question “why are you taking your medicine”
Analysis: Descriptive %, time to full disclosure

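### Both SAP power tables are labelled ICC 0.2 with 50 per clinic, but 13 of their 14 rows do not follow from that assumption

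*Combined protocol and SAP*

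**What the plan says.** The SAP has two power tables under Data Analysis.

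- **Primary outcome, sample size and power table.** The header reads "Assumptions: 80% power, alpha 0.05, ICC 0.2, average cluster size of 50". Eight combinations of mean difference and SD follow, each with the clinics needed per arm: 4, 15, 4, 9, 4, 7, 6, 9.
- **Secondary outcomes, minimum detectable differences.** The header reads "Assumption: 80% power, alpha 0.05, ICC 0.2, 10 clusters per arm, average cluster size of 50". For control proportions 0.2 to 0.7 it gives detectable values of 0.31, 0.44, 0.56, 0.69, 0.81 and 0.93.

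The SAP Summary fixes the design: "10 clinics randomized to intervention sites and 10 to control". The primary analysis is "Mixed effects linear regression to compare transition readiness scores (overall and by domain) over time in control and intervention sites", at enrollment, month 6 and month 12. The SAP gives no sidedness, rounding rule, formula, correlation over time or gain from baseline adjustment for either table.

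Protocol section 11a uses other clustering values. Aim 3 assumes "a conservative estimate of the coefficient of variation of 0.3". The Aim 1 survey assumes "an intra-class coefficient (ICC) of 0.05 and a clinic size of 50 we would need to select 102 clinics".

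**The concern.** An ICC of 0.2 with 50 patients per clinic is heavy clustering: the design effect is 1 + 49 × 0.2 = 10.8. A table that then detects half an SD with four clinics per arm looks too favourable.

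The means table is the only power basis the SAP gives for its primary outcome. If its label and its figures disagree, a reader cannot tell which clustering value the trial rests on. That bears directly on how a null result would be read: as evidence against a moderate effect, or as the product of too few clinics.

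**Working it through.** **Does the document use the standard design effect?** Yes. For Aim 1 (prevalence 60%, precision 2.5%, ICC 0.05, 50 per clinic): 1.96² × 0.6 × 0.4 / 0.025² × (1 + 49 × 0.05) / 50 = 101.8, which matches the stated 102 clinics.

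**Means table.** Clinics per arm = 2(1.96 + 0.8416)² (SD/diff)² [1 + 49 × ICC] / 50, where (1.96 + 0.8416)² = 7.849. This is two-sided, uses the normal approximation, and covers one unadjusted comparison. Row 1 at ICC 0.2: 2 × 7.849 × 4 × 10.8 / 50 = 13.56.

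| Diff / SD | Printed | ICC 0.2 | ICC 0.2, one-sided | ICC 0.2, unlimited clinic size | ICC 0.04 |
|---|---|---|---|---|---|
| 0.5 / 1 | 4 | 13.56 | 10.68 | 12.56 | 3.72 |
| 0.5 / 2 | 15 | 54.25 | 42.73 | 50.23 | 14.87 |
| 1.0 / 2 | 4 | 13.56 | 10.68 | 12.56 | 3.72 |
| 1.0 / 3 | 9 | 30.52 | 24.04 | 28.26 | 8.36 |
| 1.5 / 3 | 4 | 13.56 | 10.68 | 12.56 | 3.72 |
| 1.5 / 4 | 7 | 24.11 | 18.99 | 22.33 | 6.61 |
| 2.0 / 5 | 6 | 21.19 | 16.69 | 19.62 | 5.81 |
| 2.0 / 6 | 9 | 30.52 | 24.04 | 28.26 | 8.36 |

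No row reproduces at ICC 0.2. Neither sidedness, rounding nor clinic size closes the gap. Rounded up, the last column gives the printed figures in all eight rows. The ICC range that does so is 0.0374-0.0405 (about 0.034-0.060 across other sidedness and rounding conventions). A slip for 0.02 does not explain it either, since that gives 3, 10, 3, 6, 3, 5, 4, 6.

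**Proportions table.** At ICC 0.2 the effective sample is 500 / 10.8 = 46.3 per arm. The ICC implied by a row is (500/n − 1)/49, with n per arm from the pooled two-proportion formula. Row 1: n = 245.3, so (2.038 − 1)/49 = 0.021. The CV version is clinics = 1 + 7.849 [p0q0/50 + p1q1/50 + CV²(p0² + p1²)] / (p0 − p1)², set equal to 10.

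| Control | Printed | Detectable at ICC 0.2 | Power at printed value, ICC 0.2 | Implied ICC | Detectable at ICC 0.04 | Detectable at CV 0.2 |
|---|---|---|---|---|---|---|
| 0.2 | 0.31 | 0.472 | 23% | 0.021 | 0.334 | 0.306 |
| 0.3 | 0.44 | 0.586 | 28% | 0.035 | 0.447 | 0.433 |
| 0.4 | 0.56 | 0.686 | 34% | 0.047 | 0.552 | 0.558 |
| 0.5 | 0.69 | 0.776 | 46% | 0.078 | 0.650 | 0.682 |
| 0.6 | 0.81 | 0.856 | 60% | 0.120 | 0.743 | 0.805 |
| 0.7 | 0.93 | 0.925 | 82% | 0.214 | 0.829 | 0.928 |

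Only the last row agrees with ICC 0.2. The implied ICC rises tenfold down the column, so no single ICC fits, and the 0.04 that fits the means does not fit here. CV 0.2, rounded up, matches all six rows. It also does so with t on 18 df in place of the extra clinic.

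**Consequence at 10 clinics per arm.** Power for a standardised difference d is Φ(d / √(2 × DE / 500) − 1.96). The square root is 0.2078 at ICC 0.2 (DE 10.8) and 0.1088 at ICC 0.04 (DE 2.96).

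| d (SD units) | ICC 0.04 | ICC 0.2 |
|---|---|---|
| 0.50 | 99.6% | 67% |
| 0.40 | 96% | 49% |
| 0.375 | 93% | 44% |
| 0.33 | 86% | 36% |

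With t on 18 df these become 99, 93, 90 and 83%, and 62, 44, 40 and 33%. The detectable difference is 2.8016 × 0.1088 = 0.30 SD or 2.8016 × 0.2078 = 0.58 SD (0.32 and 0.62 with t). The remaining row (0.5, SD 2) is already printed as needing 15 clinics.

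**The case against.** The strongest reply is that ICC 0.2 was meant and the tables carry an unstated gain from repeated measures or baseline adjustment. For the means table alone this cannot be excluded. Cutting the variance to 0.26-0.29 of its unadjusted value, a clinic-mean correlation of about 0.85, would turn the ICC 0.2 column into the printed one. The two tables also serve different models (a mixed model and GEE), so they need not share one gain. But the SAP states no correlation, and the reply fails within the proportions table, whose rows would need factors from 0.16 to 1.06.

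A second reply is that the mislabelling account is not tidy. The means fit ICC 0.04 (0.2 squared) without an extra clinic and with the normal approximation. The proportions fit CV 0.2 only with the extra clinic or t; without either, CV 0.2 gives 0.299 to 0.915. Two measures and two conventions are therefore involved. This is fair, and it is why the cause remains an inference.

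Third, the SAP names no target difference, the clinics are already fixed, and under the likelier reading the printed figures broadly stand. That limits the harm, but it does not make the stated assumption and the printed figures compatible.

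**Conclusion.** The concern holds. All eight means rows and five of the six proportions rows contradict the stated ICC of 0.2. The means rows are too small by a factor of about 3.4 to 3.6. This does not depend on sidedness, rounding or clinic size.

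The likelier explanation is a wrong label rather than an underpowered trial. If ICC 0.2 is truly meant, with no gain from repeated measures or baseline, the trial is well short of 80% power for every difference the means table shows as reachable. These power figures are for one unadjusted comparison of means with equal clinics of 50. The planned mixed model could recover some power, by an amount the SAP does not allow anyone to compute.

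**What to change.** State for each table the clustering measure and value, formula, sidedness, rounding and reference distribution, and make the header and figures agree.

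- **If 0.2 was a mislabel:** correct it, for example to ICC about 0.04 for the means and CV 0.2 for the proportions. The printed figures then stand under the conventions shown above. If t is used throughout, the means column becomes 5, 16, 5, 10, 5, 8, 7, 10 and the proportions do not change.
- **If ICC 0.2 is meant:** restate the clinics per arm as 14, 55, 14, 31, 14, 25, 22, 31 (15, 56, 15, 32, 15, 26, 23, 32 with t). Give the detectable difference at 10 per arm as about 0.58 SD (0.62 with t), and the detectable proportions as about 0.47, 0.59, 0.69, 0.78, 0.86, 0.93 (first value 0.48 with t).
- **If a gain from repeated measures or baseline adjustment is relied on:** state the assumed correlation.

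A sentence relating the chosen value to the protocol's CV of 0.3 (Aim 3) and ICC of 0.05 (Aim 1) would help but is optional.

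The cost is SAP wording and up to two recomputed tables. No clinics, patients or analyses change. Under the ICC 0.2 branch the stated figures become less favourable.

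### The SAP's detectable-difference table for retention and suppression is labelled ICC 0.2 but matches a coefficient of variation of 0.2, and it stops at 0.70, below the 75-80% control retention implied by protocol Table 8

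*Combined protocol and SAP*

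**What the plan says.** The SAP's section on secondary outcomes names two. Retention is "defined as proportion of 10-24 year olds completing visits within 6 months of last visit". Suppression is "proportion of 10-24 year olds with viral load of less than 1000 copies per ml after at least 6 months of ART". Both are compared by GEE at baseline, month 6 and month 12.

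Under "Minimum detectable differences in proportions with outcomes" the SAP lists six pairs, headed arm 1 and arm 2: 0.2 and 0.31, 0.3 and 0.44, 0.4 and 0.56, 0.5 and 0.69, 0.6 and 0.81, 0.7 and 0.93. The stated basis is "Assumption: 80% power, alpha 0.05, ICC 0.2, 10 clusters per arm, average cluster size of 50".

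The protocol powers the same clinics differently in section 11a (Aim 3, Table 8). It works with LTFU rather than retention, and with a CV rather than an ICC: "This assumes alpha of 0.05, 80% power, and a conservative estimate of the coefficient of variation of 0.3". The two relevant rows read "24-month LTFU 20% 10% 7" (younger group) and "24-month LTFU 25% 15% 10" (older group): control rate, intervention rate, clinics per arm. As retention, these are 80% v 90% and 75% v 85%.

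**The concern.** There are two linked problems. The printed clustering measure is not the one behind the printed differences, so a reader who takes the label at face value is misled about power even inside the table. And the table has no row at the control retention that the protocol's Aim 3 assumptions imply, so it does not show what 10 clinics per arm can detect there.

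This matters when the results are read. A non-significant retention result could be set against a table advertising 80% power and taken as evidence that the package does not help. If clustering is anything like the label, the trial would usually miss the improvement the protocol itself targets.

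**Working it through.** **Inputs.** From the SAP: 80% power, alpha 0.05, 10 clinics per arm, m = 50 per clinic, clustering value 0.2. Sidedness is not stated; I assume two-sided, so (1.960 + 0.842)² = 7.849. Arm 1 is read as control. From protocol Table 8: retention 80% v 90% and 75% v 85%.

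**1. Which measure gives the printed table?**

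As a CV (k = 0.2), clinics per arm are c = 1 + 7.849 × [(p1q1 + p2q2)/50 + 0.04(p1² + p2²)]/(p1 − p2)².

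As an ICC of 0.2, the design effect is 1 + 49 × 0.2 = 10.8 and the effective size is 500/10.8 = 46.3 per arm. I use the unpooled two-proportion z test.

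| Printed pair | c, CV 0.2 | Arm 2 solved, CV 0.2 | Arm 2 solved, ICC 0.2 | Power of printed pair, ICC 0.2 |
|---|---|---|---|---|
| 0.2, 0.31 | 9.38 | 0.306 | 0.463 | 0.231 |
| 0.3, 0.44 | 9.20 | 0.433 | 0.577 | 0.291 |
| 0.4, 0.56 | 9.79 | 0.558 | 0.679 | 0.345 |
| 0.5, 0.69 | 9.33 | 0.682 | 0.769 | 0.475 |
| 0.6, 0.81 | 9.64 | 0.805 | 0.850 | 0.624 |
| 0.7, 0.93 | 9.86 | 0.928 | 0.919 | 0.847 |

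Under the CV reading every pair rounds up to 10 clinics, and the solved values rounded up match all six rows. Under ICC 0.2 only the last row is close. A pooled variance changes little (power 0.226 to 0.824).

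**2. Extending the table upwards.**

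| Control | ICC 0.2 | CV 0.2 on retention |
|---|---|---|
| 0.75 | 0.950 | 0.989 |
| 0.80 | 0.976 | no solution ≤ 1 |
| 0.85 | 0.998 | no solution ≤ 1 |
| 0.90 | no solution ≤ 1 | no solution ≤ 1 |

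The CV column is formal near the ceiling. Between-clinic variance cannot exceed p(1 − p), so k = 0.2 is possible only up to p = 1/(1 + 0.04) = 0.96.

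**3. Power for the protocol's 10-point gains.**

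- ICC 0.2, 80% v 90%: SE = √[(0.16 + 0.09)/46.3] = 0.0735; 0.10/0.0735 − 1.960 = −0.60; power 27%. For 75% v 85%: SE 0.0825, power 23%.
- CV 0.2 on retention, 80% v 90%: SE = √{[0.25/50 + 0.04(0.64 + 0.81)]/9} = √(0.063/9) = 0.0837; power 22%. For 75% v 85%: √(0.0577/9) = 0.0801; power 24%.
- CV 0.2 on LTFU, 20% v 10%: √{[0.25/50 + 0.04(0.04 + 0.01)]/9} = √(0.007/9) = 0.0279; power 95%. For 25% v 15%: √(0.0097/9) = 0.0328; power 86%.
- ICC 0.05, the value the protocol uses for Aim 1: 67% and 57%.
- ICC 0.02 (design effect 1.98, effective size 252.5): 89% and 81%.

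**4. How far apart the readings are.** A CV k at proportion p corresponds to an ICC of k²p/(1 − p). On LTFU of 20% and 25%, k = 0.2 gives 0.010 and 0.013. On retention of 80% and 75% it gives 0.16 and 0.12.

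**5. Table 8 as a check.** With k = 0.3 on LTFU and 100 per clinic, the formula in step 1 gives 6.49 and 9.48, hence the printed 7 and 10. With k = 0.3 at the SAP's 50 per clinic it gives 8.46 and 11.95, so 9 and 12 clinics; with 10, power is 87% and 72%.

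**The case against.** The strongest objection is that a CV depends on scale and that the protocol's only powering of this outcome is on LTFU. With the SAP's k = 0.2 applied there, LTFU of 20% v 11.9% and 25% v 15.7% is detectable, and the targeted gains are well powered. This stands, so a reader should not infer that the shortfall holds however 0.2 is interpreted. It does not rescue the table as printed: the label says ICC, the SAP defines retention and not loss, and the LTFU reading implies an ICC near 0.01, far below 0.2.

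Three other strong inferences also fail.

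- A reader might infer that the protocol expects 50-90% in the trial and that the table fails across that range. The phrase "possible ranges (50%-90%) of prevalence of retention in care or viral load suppression" belongs to the Aim 1 precision calculation and lists possibilities. The table covers 50-70% of it, with printed gains of 19 to 23 points.
- A reader might infer that no improvement from 80% could ever be shown under the CV reading, even if every patient were retained. At 100% there is no between-clinic spread, yet the formula keeps it. Dropping that term gives about 94% power for 80% v 100%. The formula is outside its valid range.
- A reader might infer that suppression is underpowered too. No Aim 3 control suppression rate is given, so this is unknown.

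Two caveats remain. The 75-80% figures are complements of 24-month LTFU, whereas the SAP measures visit-based retention to month 12, and neither document maps one to the other. The protocol also plans adjustment for baseline proportions, which could reduce between-clinic variance by an amount the documents do not give. More patients per clinic would not help at ICC 0.2: at 200 per clinic the effective size is 2000/(1 + 199 × 0.2) = 49.0, against 46.3.

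**Conclusion.** The point holds in limited form. The ICC label does not match the table. At a true ICC of 0.2 the printed pairs have roughly 23% to 85% power, and only the last reaches 80%. The table also omits the control retention implied by Table 8. There, both the labelled ICC and the retention-scale CV that reproduces the table require a rise of about 18 to 24 points where a solution exists, and give 22-27% power for the protocol's 10-point gains. Those gains are adequately powered only under much weaker clustering.

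The shortfall applies to retention at about 75% and above, and to suppression only if its control rate proves that high. It rests on two-sided testing, 10 clinics of 50 per arm, no gain from baseline adjustment, and Table 8 as a guide to control retention. These are secondary outcomes, but the table is the SAP's only power statement for them.

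**What to change.** In the SAP's secondary-outcomes section:

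1. State whether 0.2 is an ICC or a CV and, if a CV, whether it applies to retention or to LTFU. State the sidedness of alpha.
2. Recompute every row from that one measure. Keep 0.2 to 0.7, since the low rows serve LTFU or non-suppression, and add 0.75, 0.80, 0.85 and 0.90. Mark any row that is not detectable with 10 clinics per arm.
3. Add a sentence: where a 10-point gain has under 80% power, retention and suppression are reported as differences with clinic-level 95% confidence intervals, and a non-significant result is not read as absence of effect.

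The cost is a ten-row table and a few sentences, with no extra clinics, patients or data. The downside is that the stated detectable differences may become less favourable.
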